6.2 RESPONSE CRITERIA

6.2.1 Definitions

6.2.1.1 Evaluable for toxicity

All patients will be evaluable for toxicity from the time of their first treatment with [¹⁸F] FMISO up to 24 hours post injection and any adverse events including allergic reactions, FMISO extravasation, or any Grade 3 or greater AE within the 24-hour time frame post injection will be followed until resolution.

6.2.1.2 Evaluable for imaging response and inclusion in cohort of subjects

Only those patients who have measurable disease present at baseline, and who have received baseline imaging (CT or MRI) and post TACE PET imaging with [¹⁸F] FMISO and at least one follow-up visit that includes CT or MRI.

6.2.1.3 Target lesions

Only measurable lesions targeted to undergo TACE will be evaluated. A sum of the diameters (longest for non-nodal lesions) for all target lesions will be calculated and reported as the baseline sum diameters. The baseline sum diameters will be used as reference to further characterize any objective tumor regression in the measurable dimension of the disease.

6.2.2 Methods for evaluation of measurable disease

All measurements should be taken and recorded in metric notation using a ruler or calipers. All baseline evaluations should be performed as closely as possible to the beginning of TACE (cross-sectional imaging within four weeks of TACE treatment).

The same method of assessment and the same technique should be used to characterize each identified and reported lesion at baseline and during follow-up. Imaging will include one or all of the following: CT (triple phase), MRI or PET scan.

6.2.2.1 Conventional CT and MRI

This guideline has defined measurability of lesions on CT scan based on the assumption that CT slice thickness is 5 mm or less. If CT scans have slice thickness greater than 5 mm, the minimum size for a measurable lesion should be twice the slice thickness.

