1.2 BACKGROUND AND RATIONALE

1.2.1 Hypoxia and the Tumor Microenvironment

Hepatocellular carcinoma (HCC) is the sixth most common cancer across the globe and it represents the third most common cause of cancer related deaths. HCC represents 90% of primary liver cancers. Liver tumor resection or liver transplantation, are first-line treatment options for HCC. Patients who are neither a candidate for surgery or transplantation can undergo minimally invasive procedures such as local ablation or chemoembolization. Often there is tumor progression despite these treatments¹. The implications of tumor hypoxia following chemoembolization are unclear, although an association between hypoxia and more aggressive tumor phenotype is well known. As early as 1955, Thomlinson and Gray hypothesized that the presence of hypoxia may render lung cancers resistant to radiotherapy¹. Tumor hypoxia occurs when oxygen consumption is out of balance with supply, as with reduced perfusion or diffusion-limited oxygen delivery. Clinically relevant hypoxia is detected in approximately 50% of all solid tumors irrespective of their size and histological features².

Durand and Aquino-Parsons³ studied tumor perfusion in a human xenograft tumor model and observed varying degrees of overlap of fluorescent staining or changes in fluorescence intensity corresponding to significant variations in tumor perfusion over relatively short periods of time. More recently more complex mechanisms resulting in significant fluctuations in red cell flux and tumor oxygenation have been implicated as potential determinants of tumor radio-resistance and chemo-resistance^{4,5}. These fluctuations in tumor oxygenation may occur in cycles of extremely variable duration, on the order of minutes to hours, depending upon tumor type; various studies using different models have determined cycle durations of less than 2 cycles/minute⁶, cycles every 20-30minutes⁷ or 12 hours in patients imaged with PET hypoxia agents^{8,9} tumor hypoxia and TACE therapy of liver tumors.

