3.3 IMAGE ANALYSIS

Feasibility of FMISO PET imaging post-TACE will be assessed by individually characterizing FMISO uptake in treated tumors as absent, background (equivalent to normal liver), or increased relative to liver background. Lesions demonstrating any increased activity compared to background liver will be further characterized as diffusely or focally increased activity.

Changes in FMISO PET activity before and following TACE will be descriptively compared and change in peak SUV will be assessed as response to embolization.

Individual liver tumors which demonstrate progression defined by increased size and/or enhancement will be evaluated for geographic FMISO uptake correlation. CT or MRI images demonstrating progression will be registered with FMISO PET-CT images automatically using OncoNav software (developed at the Center of Interventional Oncology) to determine whether qualitatively increased or decreased FMISO uptake is observed in spatial relation to tumor progression.

Increased FMISO activity which correlates positively with tumor progression will be further quantified using calculated standardized uptake values (SUV) or tumor-to- serum activity ratio in manually selected regions of interest (ROI).

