3.5.2 General Off-Study Criteria

- Inability to complete ¹⁸F-MISO imaging
 - Patients will be considered “unevaluable” for the study if [¹⁸F] FMISO imaging is incomplete or deficient and will be replaced (see Section 6.2.1). As an example, an FMISO scan which in the opinion of the Principal Investigator does not demonstrate hepatic uptake relative to background liver activity will be considered deficient and will not be included in the data analysis.
- Patient decides to withdraw from the study

- Toxicity which prevents further imaging (e.g. renal dysfunction defined as serum creatinine >2.0mg/dl which precludes CT or MRI imaging)
- Death
- Progression of disease
- Additional treatment of primary or metastatic hepatic malignancy (i.e., transplantation, resection)

The reason for study removal and the date the patient was removed must be recorded in the study database.

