6.2.3 Response Criteria

All of the patients who met the eligibility criteria (with the possible exception of those who could not undergo ¹⁸F-MISO imaging) should be included in the main analysis of the response to the imaging agent. All conclusions should be based on all eligible patients.

For the purposes of this study, patients with baseline CT or MRI and should be re-evaluated for response per standard of care approximately 4 to 6 weeks following TACE treatment with an abdominal CT and MRI. Scanning interval may be increased to 3 months instead of 4-6 weeks if stable disease is documented on at least two successive imaging studies obtained at the 4-6 week post-TACE interval.

Response and progression of only targeted tumors will be evaluated in this study using the revised modified Response Evaluation Criteria in Solid Tumors (mRECIST) guidelines.¹⁹

Complete Response (CR)	Disappearance of any intratumoral arterial enhancement
Partial Response (PR)	At least 30% decrease in the sum of the diameters of viable (enhancement in the arterial phase) target lesions, taking the baseline sum of the diameters of target lesions

Stable Disease (SD)	Any cases that do not qualify for either PR PD
Progressive Disease (PD)	An increase of at least 20% in the sum of the diameters of viable (enhancing) target lesion, taking as reference the smallest sum of the diameters of viable (enhancing) target lesions recorded since treatment started.

European Association for the Study of Liver, European Organization for Research and Treatment of Cancer. Journal of Hepatology, 2012 56:908-943.

Serum alpha-fetoprotein levels will be assessed and compared pre- and post-TACE per standard of care as a marker for tumor progression despite TACE. Cross-sectional and PET imaging will continue to be obtained at 4-6 week intervals until imaging evidence of disease progression is obtained and compared with FMISO imaging.

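### The FMISO reading and the pre/post SUV comparison take no account of tumor size, so PET blur in a small tumor could be reported as lack of hypoxia or lack of embolization effect

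*Combined protocol and SAP*

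**What the plan says.** The feasibility reading in section 3.3 consists of "individually characterizing FMISO uptake in treated tumors as absent, background (equivalent to normal liver), or increased relative to liver background". The same section compares FMISO activity descriptively before and after TACE and treats the change in peak SUV as the response to embolization. It gives no minimum tumor size, PET resolution, partial-volume correction or class for a tumor that cannot be assessed.

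Size enters only in section 6.2:

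- 6.2.1.2 admits to the imaging-response cohort "Only those patients who have measurable disease present at baseline", among other conditions.
- 6.2.1.3 states "Only measurable lesions targeted to undergo TACE will be evaluated", and records longest diameters for the baseline sum.
- 6.2.2.1 bases "measurability of lesions on CT scan based on the assumption that CT slice thickness is 5 mm or less"; for thicker slices, "the minimum size for a measurable lesion should be twice the slice thickness". No millimetre minimum is printed for slices of 5 mm or less, or for MRI.

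Two other statements bear on the point. Section 1.2.1 says "Clinically relevant hypoxia is detected in approximately 50% of all solid tumors irrespective of their size and histological features". Section 3.5.2 says that a scan which in the Principal Investigator's opinion "does not demonstrate hepatic uptake relative to background liver activity will be considered deficient and will not be included in the data analysis".

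**The concern.** The primary objective asks whether hypoxic tumor can be identified against a liver background that the plan itself expects to be high. Contrast is therefore likely to be modest, and that is where blur matters most. A tumor that is small relative to the scanner's effective resolution loses part of its contrast to the surrounding liver, whatever its oxygenation. With only three classes available, the reader must then call it absent, background or increased, and background becomes the likely label.

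Section 1.2.1 gives no ground for presuming that small tumors are free of hypoxia. A background reading in a small tumor is thus ambiguous between no hypoxia and too small to show it. The same attenuation acts on the pre/post change in peak SUV, so differences between tumors in apparent response to embolization may partly reflect diameter. With as few as ten evaluable patients, a handful of such lesions could colour the descriptive result.

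**Working it through.** **The plan's own size rule.** Twice the slice thickness gives 12 mm at 6 mm slices, 16 mm at 8 mm and 20 mm at 10 mm. Because it applies only above 5 mm, the minimum it sets always exceeds 10 mm. The unprotected cases are slices of 5 mm or less, MRI, and any reading of 3.3 under which measurability does not apply.

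**Inputs that are assumptions.** The documents state no PET resolution, tumor sizes or expected tumor-to-liver ratio. Assumed here: effective blur (including breathing) of 6 to 12 mm FWHM; a uniformly hypoxic sphere in uniform liver; and a true tumor-to-liver ratio of 1.3, with 1.5 as an alternative.

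**Formula.** With radius R = D/2, sigma = FWHM/2.355 and x = R/sigma, the share of contrast recovered at the centre is

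RC = erf(x/√2) − √(2/π) · x · exp(−x²/2).

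Example, D = 10 mm and FWHM = 6 mm: x = 5/2.548 = 1.96; RC = 0.950 − 0.228 = 0.72. At FWHM = 12 mm: x = 0.98; RC = 0.674 − 0.484 = 0.19.

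| Diameter | FWHM 6 | FWHM 8 | FWHM 10 | FWHM 12 |
|---|---|---|---|---|
| 10 mm | 0.72 | 0.46 | 0.29 | 0.19 |
| 15 mm | 0.97 | 0.82 | 0.63 | 0.46 |
| 20 mm | 1.00 | 0.97 | 0.86 | 0.72 |
| 30 mm | 1.00 | 1.00 | 0.99 | 0.97 |

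**Effect on the reading.** Measured ratio = 1 + (true ratio − 1) × RC. A true ratio of 1.3 reads 1 + 0.3 × 0.72 = 1.22 down to 1 + 0.3 × 0.19 = 1.06 at 10 mm, and 1.30 down to 1.29 at 30 mm.

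As an illustration, suppose a reader calls a tumor increased when the measured ratio exceeds 1.1, with SD 0.08 (both assumed). The chance of that call is Φ((measured ratio − 1.1)/0.08). At a true ratio of 1.3 and 10 mm it is 93%, 68%, 44% and 30% at FWHM 6, 8, 10 and 12, against 99% throughout at 30 mm. At a true ratio of 1.5, the 10 mm figures are 100%, 95%, 72% and 47%.

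**Effect on the SUV change.** If liver uptake is unchanged between scans, measured change = RC × true change at the tumor centre. A true rise of 1.0 SUV unit would then read as 0.72 down to 0.19 in a 10 mm tumor and 1.00 down to 0.97 in a 30 mm tumor. The centre value stands in for peak SUV, which the plan does not define further.

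**Where a size mark could sit.** At D = 2 × FWHM, x = 2.355 whatever the scanner, and RC = 0.86. Twice the measured resolution is therefore a reasonable point below which attenuation becomes material.

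**The case against.** *The plan nowhere counts small tumors as negative.* A reader might infer that small tumors are scored FMISO-negative and lower an identification rate. The documents do not support this. Section 3.3 uses descriptive classes, and no lesion-level rate is defined. The only rate is the six-patient rule in 3.7, which is per patient (1/6 = 16.7% and 2/6 = 33.3%, either side of its 30%); one visible tumor appears to be enough there. Section 3.5.2 drops and replaces a patient whose whole scan shows no uptake above liver, which could push a rate up. That sits unreconciled with 6.2.3, where "All conclusions should be based on all eligible patients". What remains is the small tumor in a scan with uptake elsewhere, and the SUV comparison.

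*Measurability may already apply.* Sections 6.2.1.2 and 6.2.1.3 can be read as limiting the treated tumors of 3.3 to measurable ones, and 6.2.2.1 refers to a guideline that may supply the missing minimum. This is a fair reading. Even so, a CT measurability rule does not address what PET can show.

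*The size of the effect is all assumption.* This is correct. At 6 mm FWHM the loss of detection at 10 mm is slight (93% against 99%); the 30% figure is the worst corner of the range. Section 3.2 also allows a 240-minute scan and subtraction techniques when contrast is poor; these may raise contrast but do not remove blur.

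*A size exclusion would be wrong.* This stands too. At FWHM 10 mm a 15 mm tumor would still be called increased 86% of the time in the illustration above, so a hard 20 mm cut would discard informative lesions. Baseline diameter is also an imperfect guide: 1.2.1 expects necrosis after TACE, 10.8 says the tracer is not trapped in necrotic tissue, and 3.3 expects focal uptake. An 8 mm hypoxic focus in a 40 mm tumor has recovery of only 52% down to 11% over the same blur range.

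**Conclusion.** The concern holds in a limited form. Neither the uptake classes nor the SUV comparison in 3.3 takes account of tumor size, and the one size rule in the plan serves a different purpose. Under the stated model, a 10 mm tumor keeps 72% down to 19% of its contrast and a 30 mm tumor 100% down to 97%, so a size effect could be reported as absent hypoxia or as lack of response to embolization. These figures rest on an assumed 6 to 12 mm FWHM and a uniform sphere. The number of tumors affected cannot be estimated from the documents and may be zero. The documents do not show that the feasibility result is biased in a known direction. This is a gap in reporting and interpretation in a small descriptive pilot; it is worth closing because closing it costs little.

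**What to change.** In section 3.3:

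1. Keep all treated tumors in the FMISO reading.
2. Show uptake class and change in peak SUV against the baseline diameter already recorded under 6.2.1.3.
3. State the scanner's measured resolution. Label a tumor smaller than about twice that value, and without increased uptake, *indeterminate (size)*. Leave small tumors with increased uptake classed as increased.
4. Report the feasibility result twice: with all tumors, and with only tumors above that size. Retaining small positives while setting small non-positives aside would otherwise inflate it.
5. State that baseline diameter does not capture small hypoxic foci inside large tumors.

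Leave the CT/MRI response rule in 6.2 unchanged.

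The cost is wording, a little more tabulation and a second, secondary count in a very small sample. No new scans or measurements on patients are needed.

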6.2.3 Response Criteria

All of the patients who met the eligibility criteria (with the possible exception of those who could not undergo ¹⁸F-MISO imaging) should be included in the main analysis of the response to the imaging agent. All conclusions should be based on all eligible patients.

For the purposes of this study, patients with baseline CT or MRI and should be re-evaluated for response per standard of care approximately 4 to 6 weeks following TACE treatment with an abdominal CT and MRI. Scanning interval may be increased to 3 months instead of 4-6 weeks if stable disease is documented on at least two successive imaging studies obtained at the 4-6 week post-TACE interval.

Response and progression of only targeted tumors will be evaluated in this study using the revised modified Response Evaluation Criteria in Solid Tumors (mRECIST) guidelines.¹⁹

Complete Response (CR)	Disappearance of any intratumoral arterial enhancement
Partial Response (PR)	At least 30% decrease in the sum of the diameters of viable (enhancement in the arterial phase) target lesions, taking the baseline sum of the diameters of target lesions

Stable Disease (SD)	Any cases that do not qualify for either PR PD
Progressive Disease (PD)	An increase of at least 20% in the sum of the diameters of viable (enhancing) target lesion, taking as reference the smallest sum of the diameters of viable (enhancing) target lesions recorded since treatment started.

European Association for the Study of Liver, European Organization for Research and Treatment of Cancer. Journal of Hepatology, 2012 56:908-943.

Serum alpha-fetoprotein levels will be assessed and compared pre- and post-TACE per standard of care as a marker for tumor progression despite TACE. Cross-sectional and PET imaging will continue to be obtained at 4-6 week intervals until imaging evidence of disease progression is obtained and compared with FMISO imaging.

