3 STUDY IMPLEMENTATION

3.1 STUDY DESIGN

Fifteen patients with metastatic or primary hepatic malignancy will be enrolled to yield a minimum of ten evaluable patients. Prior to TACE, all patients will undergo conventional baseline imaging. The first five patients enrolled will receive a single dose of the study imaging agent (FMISO) post-TACE to determine imaging parameters and feasibility. Subsequent to the feasibility study, the remaining patients (#6-15) will receive the hypoxia imaging agent before and following TACE to determine changes in uptake pattern attributable to arterial embolization. Following TACE patients will be monitored according to standard of care until tumor progression is documented. Registration of functional and/or metabolic imaging demonstrating progression with immediate post-TACE hypoxia imaging will be performed for correlative analysis.

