3.4 STUDY CALENDAR

Patients will be scheduled for pre-TACE imaging up to one week before TACE and post-TACE imaging 24 to 72 hours based on their clinical condition. Patients will sign the protocol consent prior to [¹⁸F] FMISO administration and imaging. Per PET scanning protocols, patients will be NPO (≥4-6 hours) before actual scanning. Patients will obtain standard of care post-TACE imaging by their primary oncology team, however, the research team may follow up, typically, but not required with clinic visits or phone calls. Follow up imaging and tumor measurements/s are the only research-related activities to be performed until tumor progression, withdrawal from study or a new, non-TACE, treatment is indicated. If this follow-up occurs outside NIH CC, documentation must be provided to the study PI.

	Pre- ^[18F] FMISO PET Scan	^[18F] FMISO PET Scan ^{4,5}	Standard of Care and Research follow up post TACE ^{3,4,7}
Informed consent ¹	X		
^[18F] FMISO dose approximately 10mCi ⁴		X	
Primary or metastatic malignant hepatic disease ²	X		
CT/ MRI ⁴	X		X

Tumor measurements ^{4,8}	X		X
Demographics ⁴	X		
Medical history ⁴	X		X
Physical exam ⁴	X		X
Vital signs ⁴	X		X
Height ⁴	X		
Weight ⁴	X		
Creatinine ⁴	X		
B-hCG Urine or Serum ^{3,6}	X		
Adverse event evaluation		X ³	X

1. Informed consent must occur prior to any study specific procedure or scan. See also section 9.4
2. In the absence of a pathological diagnosis of hepatocellular carcinoma, the diagnosis shall be made by the combination of serum alpha-fetoprotein ≥ 200 mg/ml and CT or MRI of the liver showing an imaging appearance characteristic of hepatocellular carcinoma
3. AE evaluation will be obtained within 24 hours post TACE FMISO injection.
4. Patient must have physician willing to collaborate with NIH PI by providing required medical record and digital MR/ CT scan documentation pre and post TACE procedure. Imaging done outside NIH must be digitally provided to NIH for tumor measurement/assessment
5. NIH only
6. FMISO imaging will be performed **only** post TACE in **the first five consecutively enrolled patients** and pre and post TACE in the **remaining** patients.
7. Pregnancy test for women of childbearing potential. Test must be within 48 hours of PET scan
8. Standard of care follow up post- TACE q 4-6 weeks. Scanning interval may be increased to 3 months if stable disease is documented on at least two successive imaging studies

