8 STATISTICAL CONSIDERATIONS

The study is a proof of concept protocol. It aims to determine the feasibility of acute hypoxia imaging of the liver following TACE. Power and significance calculations are not applicable to this small sample feasibility study.

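### Patients who cannot be scanned after TACE are replaced and may leave the main analysis, so imaging failures miss the feasibility result and the uptake proportion has conflicting denominators

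*Combined protocol and SAP*

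**What the plan says.** Section 8 gives the aim in one sentence: "It aims to determine the feasibility of acute hypoxia imaging of the liver following TACE". Section 1.2.3 describes the goal of the pilot in similar terms. The primary objective in section 1.1.1 is narrower: whether hypoxic tumor can be identified against a high liver background.

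Section 3.3 assesses feasibility by placing uptake in each treated tumor in one of three classes: absent, equal to normal liver, or increased. Section 3.4 schedules "post-TACE imaging 24 to 72 hours based on their clinical condition".

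Under section 3.5.2, inability to complete FMISO imaging takes a patient off study. The patient is unevaluable if "imaging is incomplete or deficient and will be replaced". The example given is a scan that, in the principal investigator's opinion, "does not demonstrate hepatic uptake relative to background liver activity will be considered deficient and will not be included in the data analysis". The same section requires the reason for and date of each removal to be recorded.

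Section 6.2.1.2 restricts the evaluable cohort to patients with measurable disease, baseline CT or MRI, post-TACE FMISO PET and at least one follow-up CT or MRI. Section 6.2.3 puts all eligible patients in the main analysis "with the possible exception of those who could not undergo" FMISO imaging. The next sentence reads "All conclusions should be based on all eligible patients". Section 3.1 says that fifteen patients "will be enrolled to yield a minimum of ten evaluable patients".

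**The concern.** The trial asks whether the liver can usefully be imaged for hypoxia within days of TACE. A patient who has TACE but is not scanned bears on that question, and the protocol itself gives reasons to expect some. Post-embolization pain, nausea, vomiting and fever are the most common adverse effect of TACE (section 1.2.1). The patient must be able to lie still (2.1.1.7). The scan is at NIH only, although TACE may be given elsewhere (2.2).

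No section gives such a patient a result. The reported uptake would then describe only those who were well enough and near enough to be scanned. A reader would have no planned figure for how many were not. The same gap affects the one numerical decision rule, in section 3.7: enrollment is limited to six patients if fewer than 2 show uptake. That rule does not say whether an unscanned or replaced patient counts among the six.

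**Working it through.** **1. The route of an unscanned patient**

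| Section | Effect on a patient with no completed post-TACE scan |
|---|---|
| 3.3 | None of the three uptake classes can be assigned |
| 3.5.2 | Off study, unevaluable, replaced; reason recorded |
| 6.2.1.2 | Outside the evaluable cohort |
| 6.2.3, exception | May be left out of the main analysis |
| 6.2.3, next sentence | Must be in the basis for all conclusions |
| 8 | No completion measure, denominator or success criterion |

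The last sentence of 6.2.3 conflicts with the sentence before it and with 3.5.2 and 6.2.1.2. Even if it governs, nothing says how to score the patient.

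**2. The plan's own figures**

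Fifteen enrolled for at least 10 evaluable allows 15 − 10 = 5 losses, and 5/15 = 33%. Section 8 gives no formula or loss rate, so 15 cannot be derived independently. The rule in 3.7 agrees with its 30% benchmark: 1/6 = 16.7% is below it and 2/6 = 33.3% is above it.

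**3. Effect of the denominator**

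Assumptions: losses occur at the scan, all 15 are eligible and have TACE, and 6 patients show increased uptake. The 6 is my illustration, not a figure from the plan. Intervals are exact (Clopper–Pearson): for x of n, the lower limit is the 2.5% quantile of Beta(x, n − x + 1) and the upper limit is the 97.5% quantile of Beta(x + 1, n − x).

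| Unscanned | Completion (95% CI) | Uptake, scanned only | Uptake, all enrolled |
|---|---|---|---|
| 5 (upper limit) | 10/15 = 66.7% (38.4–88.2%) | 6/10 = 60.0% (26.2–87.8%) | 6/15 = 40.0% (16.3–67.7%) |
| 2 | 13/15 = 86.7% (59.5–98.3%) | 6/13 = 46.2% | 6/15 = 40.0% |

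At the upper limit the scanned-only figure is 15/10 = 1.5 times the all-enrolled figure, whatever the uptake count. With 2 unscanned the ratio is 15/13 = 1.15.

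**4. The six-patient rule**

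Let p be the true uptake proportion in scanned patients and d the proportion not scanned. If an unscanned patient counts as showing no uptake, the chance per patient is q = p(1 − d), and P(fewer than 2 of 6) = (1 − q)^6 + 6q(1 − q)^5. Assume p = 0.50.

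| d | q | P(limit enrollment to six) |
|---|---|---|
| 0, or six scanned patients required | 0.50 | 0.109 |
| 10% | 0.45 | 0.164 |
| 20% | 0.40 | 0.233 |
| 33% | 0.333 | 0.351 |

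The chance of limiting enrollment can therefore roughly triple with a denominator that the plan does not state.

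**5. Completed scans without uptake**

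Section 3.3 treats absent and background uptake as results. The example in 3.5.2 lets the investigator call a scan deficient and drop it when it shows no uptake relative to background liver. If that example is applied to a technically complete scan, a negative result leaves the analysis too, by the same route as a missed scan.

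**The case against.** The strongest reply is that the primary objective concerns detectability of signal. On that reading an unscanned patient is missing data, and leaving that patient out of an analysis of response to the imaging agent is natural. This stands in part. A reader might infer that every unscanned patient is a failure of the primary objective, and section 1.1.1 does not support that. But sections 1.2.3 and 8 state the aim more broadly, and even the narrow objective needs one denominator where the plan gives two.

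Further replies limit the point:

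- Completion could be reconstructed. Section 2.3 keeps screening and enrollment logs, and 3.5.2 records removals. The defect is that no planned analysis uses them, not that the information is lost.
- The allowance of 5 in 15 is not a forecast of scan failures, because evaluability also needs follow-up CT or MRI. A reader might infer that a third of patients will go unscanned; the documents do not say so.
- A reader might infer that the most strongly embolized patients are the ones removed. No section links extent of embolization to missing the scan. Section 1.2.1 calls the post-embolization symptoms transient, and 3.4 lets timing within the window follow the patient's condition.
- The example in 3.5.2 may have been meant for technical failure. Its wording still overlaps two of the scored classes in 3.3.

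That the study is descriptive, without power calculations, does not remove the need for a denominator. With 10 to 15 patients, each exclusion moves a proportion by several points.

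**Conclusion.** The concern holds in this form: the exclusion rule is explicit and contradicts itself. Applied as written, it keeps failures to obtain the post-TACE scan out of the planned feasibility result and leaves the uptake proportion with conflicting denominators. Safety is not affected, but the feasibility statement cannot be interpreted properly until this is settled.

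The size depends on the number unscanned, which the documents do not give. Across the illustrated range of 2 to 5 of 15, completion runs from 87% down to 67%. The gap between the two uptake figures runs from 6 to 20 percentage points. These gaps rest on the assumed count of 6 with uptake and on all losses being at the scan, so the larger one is an upper limit for that count.

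A denominator of enrolled patients alone would also miss some failures. Referral patients may consent as late as the scan itself (9.4.2), and outpatients sign on arrival (3.1.2). A patient treated elsewhere who is too unwell to travel may therefore never enroll. This matters mainly for the first five patients, because later ones need consent for a pre-TACE scan.

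**What to change.** In 6.2.3, remove the possible exception so that the two sentences agree, and name two results:

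1. **Scan completion.** Numerator: patients with a completed post-TACE FMISO scan in the window of section 3.4. Denominator: all patients confirmed eligible under section 2.2 who received TACE. Include referral patients who never reached consent, as a count from the screening log. List reasons for non-completion, and list out-of-window scans separately.
2. **Uptake.** Patients with increased uptake, over scanned patients and over all eligible, TACE-treated, enrolled patients.

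In 3.5.2, state that a replaced patient stays in the denominator of result 1. State also that a completed scan without increased uptake is a scored result under 3.3, not a deficient scan. In 3.7, state the same denominator for the six-patient rule, so that it is clear whether an unscanned or replaced patient counts among the six.

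The cost is protocol wording, one extra proportion and a log count. Section 2.3 describes the logs for enrolled patients, so it should say that they also hold patients confirmed eligible who did not enroll. Section 2.2 already brings checklists in before TACE. No clinical procedure changes. The downsides are that the reported feasibility figure may be less favorable, and that the six-patient rule is met more often if unscanned patients count as showing no uptake.
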